## 1.0 PROTOCOL SUMMARY AND/OR SCHEMA

This is a multi-center, open-label, phase 2 trial testing the efficacy and safety of 2 interventions that target rash during PI3K inhibitor therapy in postmenopausal women and men with histologically-confirmed, hormone receptor (HR)-positive, HER2-negative, PIK3CA mutant metastatic breast cancer (MBC). A total of 63 patients will be enrolled into one arm: benralizumab 30mg in combination with standard of care (SOC) endocrine therapy (fulvestrant or AIs or aromatase inhibitors (AIs)) and PI3K inhibition (alpelisib). A total of 43 patients will be enrolled at MSKCC and a total of 20 patients will be enrolled at the participating external institutions (10 patients at Stanford University and 10 patients at Dana Farber Cancer Institute). The primary endpoint is the proportion of patients with grade  $\leq 1$  rash rate at 4 weeks.

**Patient Population:** The primary study population will be postmenopausal women and men with histologically-confirmed, HR-positive, HER2-negative, *PIK3CA* mutant MBC who have received no more than 2 lines of endocrine-based therapy in the metastatic setting.

**Design:** A multi-center, open-label, phase 2 trial testing the efficacy and safety of one interventions (one anti IL-5 receptor antibody and one antihistamine) that target the maculopapular rash during PI3K inhibitor therapy in patients with HR-positive, HER2-negative, *PIK3CA* mutant MBC receiving first or second line therapy. Study participants (n=112) will enrolled to one arm: benralizumab (anti-IL5ra) in combination with SOC endocrine therapy (fulvestrant or AIs) and PI3K inhibition (alpelisib). The primary endpoint is the grade  $\leq 1$  rash rate at 4 weeks. The study size is determined to compare the grade  $\leq 1$  rash rate at four weeks with historical controls. It has been reported that approximately 34% of patients receiving alpelisib will develop  $\geq$  grade 2 rash within the first 30 days. The corollary is that 66% of historical controls will have grade  $\leq 1$  rash within the first 30 days. An increase in rash control to approximately 88% is deemed to be clinically meaningful with the investigational agent under investigation (IL5r antibody). A sample size of 57 patients per group will achieve an 80% power to detect an odds ratio of 4.0 with respect to the primary endpoint. The proportion in the experimental group is assumed to be 0.66 under the null

hypothesis and 0.88 under the alternative hypothesis. The proportion is 0.66. If it is assumed that 10% of patients will withdraw consent or be lost to follow up, then 63 patients will need to be enrolled into this trial.

**Treatment Plan:** All participants will receive SOC endocrine therapy (fulvestrant or AIs) and PI3K inhibition (alpelisib). Participants will receive benralizumab 30mg subcutaneously on day -1. All participants will be monitored at regular visits for the duration of the trial. After 4 weeks, patients will be followed for safety at 90 days and disease progression for 1 year.

**Estimated Time to Completion:** 1 years.

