## 2.0 OBJECTIVES AND SCIENTIFIC AIMS

**Primary Objective:** To determine if prophylactic IL-5 receptor inhibition results in a lower incidence of alpelisib rash when compared to historical controls.

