## 4.0 OVERVIEW OF STUDY DESIGN/INTERVENTION

### 4.1 Design

This is a prospective, MSK investigator-initiated, multi-center, open-label, phase 2 trial testing the efficacy and safety of one interventions that targets interleukin 5 receptors during PI3K inhibitor therapy in patients with HR-positive, HER2-negative, *PIK3CA* mutant MBC receiving first or second line therapy. Study participants (n=63) will be treated with benralizumab in combination with SOC endocrine therapy (fulvestrant or AIs) and PI3K inhibition (alpelisib). Crossover will not be allowed. The primary endpoint is the grade ≤1 rash rate at 4 weeks.

Postmenopausal women and men with histologically-confirmed, HR-positive, HER2-negative, *PIK3CA* mutant MBC who have received no more than 1 line of endocrine-based therapy in the metastatic setting will be eligible. Study recruitment will be done by MSK and the participating institutions. Patients will be screened by members of the institution's breast oncology service. Those deemed eligible will complete baseline skin exam, skin tape stripping, blood work and urinalysis (See section 9.0).

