### Rash

Table 2. Dose modification and management for rash.

Grade	Recommendation
Grade 1  Macules/papules covering <10% BSA with or without symptoms (e.g., pruritus, burning, tightness)	No dose adjustment required.  OTC moisturizers and sun protection
Grade 2  Macules/papules covering 10 - 30% BSA with or without symptoms (e.g., pruritus, burning, tightness); limiting instrumental ADL; rash covering > 30% BSA with or without mild symptoms	No dose adjustment required.  OTC moisturizers and sun protection
Grade 3 Macules/papules covering >30% BSA with moderate or severe symptoms; limiting self care ADL	Interrupt alpelisib.  Prednisone 50mg a day over 10 days (with pneumocystis prophylaxis and PPI). Restart alpelisib as per package insert.
Grade 4 (SJS/TEN)  Life-threatening consequences; urgent intervention indicated	Permanently discontinue alpelisib, consult with dermatologist

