## 12.0 CRITERIA FOR REMOVAL FROM STUDY

- 1) > 2 consecutive weeks of a delay in treatment due to toxicities
- 2) Progressive disease (breast cancer)
- 3) Unacceptable toxicity
- 4) Intercurrent, non-cancer related illness that prevents continuation of protocol therapy or follow-up
- 5) Major protocol violation that would render the patient inevaluable for efficacy
- 6) Repeated non-compliance by the patient with protocol requirements
- 7) Changes in the patient's condition or study intervention related toxicity such that, in the opinion of the investigator, continued participation in the protocol would compromise patient well-being
- 8) Withdrawal of patient's consent for personal reasons
- 9) Death

We do not expect any of the above criteria to occur with high frequency as the 4 week PFS for this population is over 90%. All participants for whom we are able to obtain the 4 week primary endpoint (had rash event prior to 4 weeks) will be considered evaluable for the primary rash endpoint under the intention-to-treat (ITT) approach.

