## 13.0 CRITERIA FOR OUTCOME ASSESSMENT AND ENDPOINT EVALUABILITY

### 13.1 Criteria for Therapeutic Response/Outcome Assessment

To assess subjects in the Benralizumab achieving treatment success, defined as grade  $\leq 1$  rash rate at 4 weeks, as assessed by the NCI CTCAE v5.0.

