## 14.0 BIOSTATISTICS

### Sample Size

This will be a single arm trial. The target sample size is intended to test the hypothesis that benralizumab reduces the frequency of grade  $\geq$  grade 2 rash at 4 weeks relative to the historical controls in patients receiving alpelisib. The primary endpoint in the current study will be the proportion of patients to achieve a rash grade of 1 or less. It has been reported that approximately 34% of patients receiving alpelisib will develop  $\geq$  grade 2 rash within the first 30 days. An increase in rash control to approximately 88% is deemed to be clinically meaningful with the investigational agent. Sample sizes of 57 patients achieves an 80% power to detect a difference based on a two sample proportions test. Due to potential attrition during the course of the study, the sample size will be increased by 10%. The resultant sample size will be 63 patients.

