### General Statistical Plan

There will be one analysis population for the current study. The modified intent to treat (ITT) population will be all patients regardless of treatment compliance for whom investigators were able to obtain a 4-week efficacy assessment. The safety population will be patients who received at least one dose of study drug or the standard of care, regardless of any efficacy assessments. All efficacy analyses will be based on the modified ITT population. Patient, clinical and safety data as well as primary, secondary and exploratory endpoints will initially be presented descriptively as means, medians, or proportions with appropriate measures of variance (i.e. range, SD, 95%CI). The primary endpoint,  $\geq$  grade 2 rash versus  $<$  grade 2 rash will be evaluated using generalized linear models (GLIM), with a logit link function and a Bernoulli distribution. A group\*time interaction will be included to assess the difference in the outcome measure at the specific study time points. Differences in the frequency of grade 0/1 rash overall all study visits (days 14, 28 and 90) will be assessed using mixed models for repeated measures as a secondary analysis.

The total number of dose reductions and delays between study groups over the trial period will be compared using Poisson regression analysis. The absolute difference in the FACT-B and PRO-CTCAE scores from day 1 to 14 and 28 between groups will be also be evaluated using repeated measures mixed models. The cumulative dose of corticosteroid use between

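### The primary endpoint is rash grade at the 4-week visit, but its 66% null is freedom from grade 2+ rash over 30 days, so a rash that settles early can count as a success

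*Combined protocol and SAP*

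**What the plan says.** Section 4.1 states: "The primary endpoint is the grade ≤1 rash rate at 4 weeks". Section 13.1 defines treatment success in the same terms: "rash rate at 4 weeks, as assessed by the NCI CTCAE v5.0". The Sample Size text in section 14.0 frames the hypothesis as grade 2+ rash at 4 weeks and then says: "The primary endpoint in the current study will be the proportion of patients to achieve a rash grade of 1 or less". Under the General Statistical Plan, the efficacy population is patients "for whom investigators were able to obtain a 4-week efficacy assessment", and the analysis across days 14, 28 and 90 is secondary. Section 11.0 gives the day 28 visit a window of ± 7 days.

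The benchmark is a different quantity. Section 1.0 sets it directly after the endpoint: "rash rate at four weeks with historical controls. It has been reported that approximately 34% of patients receiving alpelisib will develop" grade 2+ rash in the first 30 days. Section 14.0 repeats the 34%, and section 1.0 takes the complement, 66%, as the null.

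Two places lean towards a cumulative endpoint. The primary objective in section 2.0 is whether prophylaxis "results in a lower incidence of alpelisib rash when compared to historical controls". Section 12.0 says that patients whose 4-week endpoint can be obtained, glossed as those who "had rash event prior to 4 weeks) will be considered evaluable for the primary rash endpoint", are evaluable.

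**The concern.** Grade at a visit is a status on one day. Developing grade 2+ rash within 30 days is an event that, once it has happened, cannot be undone. A patient with grade 2 rash on day 12 who is at grade 1 on day 28 succeeds under the endpoint as written and fails under the benchmark.

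If the visit is held by day 30, this difference can only raise the trial's success rate relative to 66%. A visit on days 31–35 could also catch a rash that the 30-day benchmark does not count, which works the other way.

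The trial is open-label and single-arm, so no concurrent control shares the scoring rule. Any mismatch between the endpoint and the 0.66 goes straight into the primary result. It also blurs the question: status at the visit cannot separate prevention of rash, which is the stated objective, from rash that came and resolved.

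**Working it through.** **Inputs from the documents.** Null success 0.66 (1 − 0.34), alternative 0.88, n = 57, power 80%, two-sample proportions test, 10% attrition (sections 1.0 and 14.0). Visit window: 28 − 7 = day 21 to 28 + 7 = day 35 (section 11.0).

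**Not in the documents.** Alpha, sidedness, the size of any historical group, the grade split of the 34%, and f, the share of grade 2+ rashes back to grade 1 or less at the visit. These are assumed or shown as a range.

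**The plan's own figure.** The pooled two-sample formula for 0.66 v 0.88, with two-sided 0.05 assumed and no continuity correction, gives 57 per group with 80.5% power. Then 57 × 1.10 = 62.7, or 63. The stated size reproduces under that assumption.

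**Can rash settle before the visit?** Section 3.4 gives a median onset of 13 days for grade 3–4 rash in the pivotal trial. Table 2 in section 10.0 pairs interruption of alpelisib for grade 3 rash with "Prednisone 50mg a day over 10 days". A course started at the median onset would end about day 13 + 10 = 23, inside the visit window. For grade 2, Table 2 lists only moisturizers and sun protection. The documents therefore show that early resolution is possible, not how common it is.

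**Effect of f.** For an inert drug, the success rate at the visit is p = 0.66 + 0.34f. The number of patients rescored as successes is 57 × 0.34 × f = 19.4f. Two settings were computed, both with true historical success 0.66:

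- Two-sample: pooled z test, 57 v 57, two-sided 0.05, full enumeration, counting only results in the drug's favour. Power for 0.66 v 0.88 is 82%.
- One-sample: exact binomial test, n = 57, p0 = 0.66, one-sided 0.025. Success needs at least 45 of 57, with P(X ≥ 45 at 0.66) = 2.4%.

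| f | p | Patients rescored | False positive, two-sample | False positive, one-sample |
|---|---|---|---|---|
| 0 | 0.660 | 0 | 2.6% | 2.4% |
| 5% | 0.677 | 1.0 | 4.0% | 4.3% |
| 10% | 0.694 | 1.9 | 6.0% | 7.4% |
| 25% | 0.745 | 4.8 | 17% | 27% |
| 50% | 0.830 | 9.7 | 56% | 84% |

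The false-positive rate reaches 10% at f = 17% (two-sample) or f = 13% (one-sample). An inert drug reaches the 88% target when f = (0.88 − 0.66)/0.34 = 65%.

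**The case against.** The strongest reply is that a cumulative endpoint was meant all along. Section 1.0 moves from the 4-week rate to the 30-day benchmark as if they were one quantity. The objective speaks of incidence and the drug is given as prophylaxis. The section 12.0 remark about an earlier rash event makes most sense if that event settles the outcome. No section says that a resolved rash is a success.

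This stands as evidence of intent, but it does not close the gap. Section 12.0 says who is evaluable, not how they are scored, and it differs from section 14.0, which requires a 4-week assessment. If the intent is cumulative, the success definition in section 13.1 does not say so. If the intent is visit-based, 0.66 is the wrong null. Either reading needs a change.

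It is also fair that f is unknown and could be small, and that neither test above is the planned analysis, a logit model with a group-by-time term. The percentages are illustrations, not properties of this trial. Even so, about one rescored patient in 57 (f = 5%) raises the error rate in both settings.

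The day 14 exam, the all-visit analysis and the time-to-rash analysis would show early rash. They are secondary and do not repair the primary comparison.

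**Conclusion.** The concern holds. As worded, the primary endpoint and its null measure different things, and no scoring rule connects them. This must be fixed before the primary result can be compared with 66%.

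The conclusion that the definitions differ rests on the text alone. The size of the harm rests on two conditions: that the endpoint is applied as written, and that some grade 2+ rashes settle before the visit. Under those conditions, with the alpha levels assumed above, a modest f of 10% already more than doubles the false-positive rate in both settings, and f of 13–17% takes it to 10%. Leaving the rule open would also allow the scoring to be chosen after the data are seen.

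**What to change.** Reconcile sections 1.0, 4.1, 12.0, 13.1 and 14.0 with one definition. Primary failure: any CTCAE v5.0 grade 2+ rash with onset from alpelisib day 1 to day 30, regardless of later resolution. Take the worst grade from the adverse event record and the day 14 and day 28 exams. A patient with such an event is a failure even without a day 28 visit. Keep grade at the day 28 visit as a secondary endpoint. This leaves 0.66 and 57 as stated.

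The alternative is to keep the visit-based endpoint and replace 0.66 with a justified historical day 28 prevalence. In either case, state alpha and sidedness.

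The cost is an amendment to the wording. Skin exams and adverse event evaluation at days 14 and 28 are already scheduled, but the adverse event record must hold onset date and worst grade. There are three downsides:

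- The observed success rate may be lower.
- If the day 28 visit falls on day 21, up to 30 − 21 = 9 days rest on adverse event reports, because the next scheduled visit is day 90.
- The match to 0.66 also assumes that the historical 34% was ascertained in a similar way, which the sponsor should confirm from its source.

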Previous analyses suggests that histamine producing cells and eosinophils have some role in alpelisib-related rash. All patients receiving alpelisib have a trend towards increased eosinophils, with a more pronounced effect in patients with rash. Interestingly, pre-treatment absolute eosinophil count may be lower in patients who develop rash. We also found that patients developing rash had a statistically significant increase in eosinophils after 2 weeks of

receiving alpelisib ( $p < 0.05$ ) (below, left). This has also been demonstrated in phase 1

study of alpelisib in combination with fulvestrant or Als (below, right). Prospective analyses and anecdotal experience at MSK with over 100 patients has revealed that 90% of rash develops within the first 4 weeks. Indeed, the median time to onset of grade 3-4 rash was 13 days in the pivotal SOLAR-1 trial.

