### **Benralizumab**

Benralizumab is FDA approved as a maintenance treatment of patients 12 years or older with severe asthma and an eosinophilic phenotype and will be provided by AstraZeneca. Benralizumab use in this study will be IND exempt (request submitted) The pathology of severe asthma with eosinophilic phenotype is also denoted as TH2-high phenotype.

a. Dosage and administration

Benralizumab is an IL-5R inhibitor to be administered as a single dose of 30mg subcutaneously at least 1 day and no more than 7 days prior to alpelisib initiation.

b. Preparation

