## 10.0 TREATMENT/INTERVENTION PLAN

Patients will receive fulvestrant or AIs 500 mg IM on days 1, 15, 29 and once monthly thereafter. Alpelisib 300mg by mouth once daily will be initiated with the first fulvestrant or AIs dose (day 1). Patients will continue alpelisib and endocrine therapy until disease progression or unacceptable toxicity as determined by their treating clinician.

Patients will receive benralizumab on day -1 to -7 of alpelisib initiation. Skin tape strips and research blood will be collected prior to alpelisib initiation.

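### The week-4 primary endpoint cannot separate prevention of rash from postponement, yet the primary objective claims lower rash incidence with no time limit

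*Combined protocol and SAP*

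**What the plan says.** Section 2.0 states the primary objective without a time limit: "To determine if prophylactic IL-5 receptor inhibition results in a lower incidence of alpelisib rash when compared to historical controls". Section 1.0 defines success at one time: "The primary endpoint is the proportion of patients with grade" 1 or lower rash at 4 weeks. Section 13.1 agrees.

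Exposure to the two drugs differs in length. Section 5.0: "Benralizumab is an IL-5R inhibitor to be administered as a single dose of 30mg subcutaneously", given before alpelisib starts. Section 10.0: "Patients will continue alpelisib and endocrine therapy until disease progression or unacceptable toxicity".

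The reason for week 4 is in Section 3.4, where the sponsor's experience with over 100 patients "has revealed that 90% of rash develops within the first 4 weeks". No rash grade and no end of follow-up are attached to that figure.

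The Treatment Plan in Section 1.0 describes the later follow-up: "After 4 weeks, patients will be followed for safety at 90 days and disease progression for 1 year". After Day 28, Table 9 has one more clinic visit, at Day 90. It includes a skin exam, adverse event evaluation, concomitant medications and questionnaires. Day 365 is a chart review only. Section 14.0 uses Day 90 in a secondary analysis: "Differences in the frequency of grade 0/1 rash overall all study visits (days 14, 28 and 90) will be assessed" with mixed models for repeated measures.

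Time to rash is also planned (Kaplan-Meier, log-rank, Cox), with no horizon or censoring date. Its event is grade ≥2 rash in secondary objective 4, rash of unstated grade in Section 13.2, and grade 1 or 2 rash in Section 14.0.

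**The concern.** If one dose before alpelisib shifts rash later without preventing it, the week-4 proportion improves in the same way as under true prevention. The 90% figure does not settle this. It is general alpelisib experience and is not stated to come from patients given prophylactic benralizumab. A drug chosen because it acts on the suspected mechanism may also change the timing of onset.

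The secondary analyses do not clearly close the gap. A grade ≥2 rash that starts after the Day 28 visit and resolves before Day 90 is grade 0/1 at all three visits. It therefore counts as rash-free in the visit-day model. A log-rank or Cox comparison can favour a drug that only delays onset, and the plan does not say how far the time-to-rash curve runs.

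What is at stake is the conclusion. Section 3.5 argues for the drug on the ground that it would avoid alpelisib interruptions and maintain dosing. Postponed rash would not deliver that, but the primary test could still pass.

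**Working it through.** **Inputs from the documents.** Historical grade ≥2 rash within 30 days is 34%, so the reference success rate is 0.66. The target is 0.88 with n = 57, enlarged to 63 (Sections 1.0 and 14.0). The share of rash arising within 4 weeks is 90% (Section 3.4).

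**Assumptions.** Section 14.0 states no alpha, so I take one-sided 2.5% and an exact one-sample binomial test. I treat week-4 failure as any grade ≥2 rash by week 4, to match the 30-day benchmark. The postponed fraction s is hypothetical.

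**1. The plan's own figure.** Two proportions, two-sided 5%, pooled variance, mean proportion 0.77:

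n = [1.96·√(2·0.77·0.23) + 0.842·√(0.66·0.34 + 0.88·0.12)]² / 0.22² = (1.166 + 0.484)² / 0.0484 ≈ 56.3, so 57 per group, with power 80.5%. Then 57 × 1.1 = 62.7, so 63. Both figures reproduce. (That 57 is the per-arm size of a two-arm comparison is a separate matter.)

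**2. Week-4 result for a drug that only delays.** The smallest cutoff with P(X ≥ r | 57, 0.66) ≤ 0.025 is r = 45 (actual size 0.024). If a fraction s of early grade ≥2 rash moves past week 4 and none is prevented, week-4 success is 1 − 0.34·(1 − s).

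| s postponed | Week-4 success | P(at least 45 of 57) |
|---|---|---|
| 0 | 0.66 | 2.4% |
| 25% | 0.745 | 27% |
| 50% | 0.83 | 84% |
| 65% (0.22/0.34) | 0.88 | 98.4% |

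The last row is simply the power of this test at the design target. Read instead as a two-sample test with 57 controls at 0.66, the chance in that row is 80.5%, from step 1. Neither test can tell why the rate is 0.88.

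**3. Eventual total.** If the 90% applies to grade ≥2 rash, the historical total is 0.34/0.90 = 37.8%. If 100% to 80% of rash is early, the range is 34% (0.34/1.00) to 42.5% (0.34/0.80). A delay-only drug leaves this total unchanged.

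**4. What the Day 90 grade would see.** In the 65% row, late rash affects 0.22 + (0.378 − 0.34) = 25.8% of patients, or about 15 of 57. Assume onset uniform over days 28 to 90 (62 days) and episodes of 7 to 28 days. The share still active on Day 90 is then 7/62 = 11% to 28/62 = 45%, or about 2 to 7 patients. The onset pattern and duration have no source in the documents, and longer episodes would be seen more often.

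**The case against.** The case on the other side is substantial, and much of it stands.

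A reader might infer that rash after week 4 is seen only as the grade on Day 90. The documents do not support that. Section 4.2 monitors all serious and non-serious adverse events. Table 9 schedules adverse event evaluation and concomitant medications at Day 90. Section 14.0 compares corticosteroid dose and dose reductions or delays over the whole study or trial period; only relative dose intensity stops at 4 weeks. The Kaplan-Meier analysis is not truncated at week 4, and pure delay would appear as curves that converge. The primary model also has a group-by-time interaction, and endpoints are first presented descriptively, so visits need not be viewed only in combination. What remains is that no rule turns these data into cumulative incidence: no horizon, no single event definition, and no clinic visit between Day 28 and Day 90.

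Section 14.0 already frames its hypothesis at 4 weeks. That is correct, and it makes the objective partly a wording matter. But the objective is the sentence on which a conclusion will be modelled.

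A reader might also infer that benralizumab probably only postpones rash. No document shows this. The nearest evidence points the other way: in 17 patients treated for existing alpelisib rash, rash did not recur after steroids stopped and alpelisib was rechallenged (Section 3.5). That was treatment rather than prophylaxis, with the outcome defined at week 4 and no stated follow-up for recurrence. It leaves the question open.

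Finally, Day 90 may be too early to expose every delayed rash. The lasting eosinophil and basophil reductions in Section 3.6 followed repeated dosing, and differential counts here stop at Day 28, so the duration of effect of one dose is unknown. Day 90 is the last scheduled skin exam and therefore the practical limit.

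**Conclusion.** The concern holds in a limited form. The primary endpoint supports a statement about rash through 4 weeks. It does not support the objective's unlimited claim of lower incidence, and the secondary analyses as written do not reliably fill the gap.

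The 84% to 98% range shows that the primary test would not detect the difference if half or more of early grade ≥2 rash were postponed. It is not an estimate that this will happen. It rests on an assumed postponed fraction, an exact one-sample test that the plan does not name, and an assumed one-sided 2.5% level. With 25% postponed the chance falls to 27%.

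The 38% total might be read as the Day 90 benchmark. It is not one: the 90% behind it has no grade and no follow-up limit, and rests partly on anecdotal experience. It can serve only as a rough reference for the eventual total.

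The change is worth making because it needs no new visits and alters what the trial may conclude.

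**What to change.** In Section 14.0:

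- Make grade ≥2 rash the time-to-rash event, as in secondary objective 4, and align Section 13.2.
- Set the horizon at Day 90, using adverse event onset dates and the Day 90 skin exam, and state the censoring rule.
- Report cumulative grade ≥2 incidence at Days 28 and 90 with 95% confidence intervals, beside the visit-day model.
- Compare Day 90 with the control cohort's own Day 90 figure if there is one. Otherwise report it descriptively, quoting about 38% (range 34% to 42.5%) only as a rough eventual total and not as a decision threshold.

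In Section 2.0, the repeated objective in Section 3.7 and the eventual conclusion, word the primary claim as rash through 4 weeks.

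The cost is a short amendment to the analysis text and the objective wording, with no added patients, visits or procedures. The downside is that rash between Day 28 and Day 90 depends on patients' recall and on how well adverse event onset is dated, so the Day 90 figure may be too low.
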